7.0 ASSESSMENT OF RESPONSE

7.1 MRI protocol: Precontrast sequences (T1 in- and out-of-phase, T2 fat saturated, T2 HASTE, diffusion using 3 b-values: 50-400-800, T2*) and dynamic pre- and post-contrast 3D T1-weighted imaging using Gadoxetic acid contrast (Eovist, Bayer) at the arterial, portal venous, late venous, and hepatobiliary phases will be obtained for all patients. GFR will be measured prior to examination.

7.2 MRI will be obtained every 3 months following completion of SBRT to assess for tumor response as well as to identify and monitor any additional sites of disease. MRIs will be obtained at 3, 6, 9, and 12 months.

7.3 Modified RECIST (mRECIST) will be used to assess response (Appendix B). Additional components such as extent of tumor necrosis will be used at the discretion of the radiologist.

[figure not shown]
7.4 DWI will also be utilized at the discretion of the radiologist to assist tumor response and progression.

8.0 STATISTICAL ANALYSES

8.1 Sample Size

In March 2020, we increased our target enrollment goal from 30 patients to 40 patients. A more recent systematic review with data from more than 10,000 patients with HCC undergoing TACE found that the objective response rate (ORR) was 52.5%¹ which is greater than the ORR of 35% assumed in our original sample size calculation. If we assume the proposed treatment regimen of TACE+SBRT to be ineffective in this patient population if the ORR is less than 52% and continue to consider the proposed treatment regimen effective if it can improve the ORR to at least 75%, then increasing the sample size to 40 patients yields 82% power with a type I error rate of 0.05 to detect an ORR >75% using a two-sided exact test for one proportion.

Study treatment will consist of three parts: a TACE, followed by another TACE after one month, followed in approximately 2 weeks by 5 radiation treatments given every other day. After the treatments, the subject will be followed with clinical exams, blood work, and MRIs approximately every three months up to one year. The full duration of a participant's time on study is 14 months. A timeline of the treatment is as follows:

The overall study timeline will be approximately 7 years to completion, resulting in publication. The study was initially IRB approved on 11/18/2014 with a target enrollment of 17 patients. The modification to increase the target enrollment to 30 patients was IRB approved on 11/8/2016 in the continuation submission. The 30th patient was enrolled on 11/19/2019. Primary analyses are being done as of this submission and we anticipate having a preliminary manuscript submitted by May 2020. With the additional enrollment goal, there will likely be subsequent analyses after the initial publication. The additional 10 patients will be enrolled in the next 12-18 months and will be used to strengthen the study results. With this additional enrollment and study timeline extension, we anticipate enrollment to close by mid-2021 and the study to close by early 2022 or become a phase II trial.

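### The stated 5% error and 82% power belong to one test at 40 patients, but primary analyses are already under way, apparently on 30, and the plan does not say which analysis decides.

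*Combined protocol and SAP*

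**What the plan says.** Section 8.1 (Sample Size) records the change of target: "In March 2020, we increased our target enrollment goal from 30 patients to 40 patients". The reason given is a systematic review of TACE reporting an ORR of 52.5%, "which is greater than the ORR of 35% assumed in our original sample size calculation". The regimen is now taken "to be ineffective in this patient population if the ORR is less than 52" percent, and the authors "continue to consider the proposed treatment regimen effective if it can improve the ORR to at least 75" percent. The stated operating characteristics are for 40 patients: 82% power, type I error 0.05, two-sided exact test for one proportion.

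On timing, the same section says: "The 30th patient was enrolled on 11/19/2019". It continues: "Primary analyses are being done as of this submission and we anticipate having a preliminary manuscript submitted by May 2020". After the extra 10 patients, "there will likely be subsequent analyses after the initial publication".

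Section 8.2 (Data Analysis) names a one-sample binomial test of the one-year response rate. It gives no null value, alpha, sidedness, sample size or data cut. Section 1.2.1 defines the primary objective as ORR up to 1 year, and section 7.2 schedules MRIs at 3, 6, 9 and 12 months after SBRT.

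**The concern.** An error rate and a power describe a procedure. The figures in 8.1 describe one test, done once, on 40 patients against 52%. The procedure in the same section has an earlier analysis, labelled primary, and probably a later one. The plan does not say whether the early analysis may support a claim of success, which benchmark it uses, or whether the 40-patient result replaces it.

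Two things are at stake. If the early analysis can claim success, the stated alpha and power no longer describe how the trial reaches its conclusion. And the early data are immature for an endpoint that runs to one year, so an early ORR could differ from the final one simply because the later patients have not had their scans.

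**Working it through.** **Inputs.** From 8.1: N = 40, null 0.52, alternative 0.75, two-sided exact test at 0.05, superseded null 0.35, 30th enrolment on 11/19/2019, 14 months on study per participant. Treatment and MRI timing come from Appendix D and 7.2. That the early analysis covers 30 patients is inferred from the enrolment date and the 10 additional patients; it is not stated.

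**1. The plan's own figure.** With X ~ Bin(40, p), find the smallest c with P(X ≥ c | 0.52) ≤ 0.025.
- c = 27 gives 0.0346, too large; c = 28 gives 0.0160.
- Success is therefore 28/40 (70.0%) or more.
- Power = P(X ≥ 28 | 0.75) = 0.821, which reproduces the stated 82%.
- The lower region is 14/40 or fewer, with probability 0.0228. Actual two-sided error is 0.0160 + 0.0228 = 0.0388.

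**2. The same test at 30 patients.** With X ~ Bin(30, p):
- Against 52%, c = 21 gives 0.0353 and c = 22 gives 0.0143, so the bar is 22/30 (73.3%). Power at 75% is 0.674.
- Against 35%, c = 16 gives 0.0301 and c = 17 gives 0.0124, so the bar is 17/30 (56.7%). Power at 75% is 0.992.
- Hence 17 to 21 responders out of 30 is significant against one null and not against the other.

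**3. Two looks, both against 52%.** Let X be responders among the first 30 and Y ~ Bin(10, p) among the next 10. A success claim at either look has probability P(X ≥ 22 or X + Y ≥ 28). At p = 0.52 this is 0.0143 + 0.0160 − 0.0076 = 0.0227.

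| Procedure, true ORR 52% | Upper tail | Two-sided |
|---|---|---|
| One test at 40 | 1.60% | 3.88% |
| Two looks, equal-tail exact | 2.27% | 4.96% |
| Two looks, minimum-likelihood exact | 2.27% | 6.18% |

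The two exact versions share the same upper regions. They differ only in the lower region at 30 patients (9 or fewer against 10 or fewer), so the move from 4.96% to 6.18% is entirely lower-tail.

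**4. Scenario: early look against 35%.** P(X ≥ 17 | 30, 0.52) = 0.372. Also, reaching 28/40 requires at least 28 − 10 = 18 responders among the first 30. The final test could then not succeed unless such an early test already had.

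**5. Maturity.** Assume first TACE on the enrolment date and the shortest Appendix D windows: 3 weeks to the second TACE, 1 more week to SBRT, then five fractions every other day. SBRT for the 30th patient ends in late December 2019. The 3-month MRI then falls in late March 2020, the 6-month MRI in late June 2020 and the 12-month MRI in late December 2020. Counting 14 months from enrolment gives January 2021. At a May 2020 submission, this patient could have had at most one of four response MRIs.

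**The case against.** The strongest reply is that the plan already contains one fully specified test (40 patients, 52%, exact, two-sided, 0.05) and calls the May 2020 manuscript preliminary. That manuscript was anticipated, not reported as done, and the later analyses are only likely. In a non-randomized pilot study, a reader can take the 40-patient test as the one that counts. Much of this stands: what is missing is an explicit statement, not a design. But the early analyses are labelled primary, and 8.2 does not point to the 40-patient test.

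It can also be said that multiplicity is minor. For a success claim this is right: 2.27% is still below 2.5%. A reader might infer serious inflation of false success claims from repeated testing; under the exact test named in 8.1 the numbers do not support that.

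A reader might also infer that the early report is to be judged against 35%. No section says so, and the same paragraph replaces 35% with 52%. Moreover, rejecting 35% when the true ORR is 52% is a correct rejection of that null; it misleads only if presented as evidence that the regimen is effective by the revised standard.

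On maturity, ORR up to 1 year may mean best response within the year, so a response at 3 months would already count. This softens the point without removing it: 8.2 speaks of a one-year response rate, and under either reading patients without a response still have scans to come.

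**Conclusion.** The concern holds in a limited form. The stated alpha and power apply to the 40-patient test only, and the plan does not give the role or the null of the analysis already under way. A 30-patient test against 52% has 67% power, not 82%. Two looks against 52% raise upper-tail error from 1.60% to 2.27%, and two-sided error from 3.88% to between 4.96% and 6.18% depending on the exact test. The 37% is a scenario that depends on a null the documents do not assign to the early look.

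The result assumes that the early analysis covers 30 patients and that either look may claim success. How many of the 30 lacked one-year data cannot be derived, because no accrual dates are given apart from the 30th; that the last of them did follows from the protocol's own timeline.

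A reader might infer that the null and sample size were changed in response to results. The documents do not support this: the stated reason is an external review, the change raised the bar from 35% to 52%, and nothing says whether response results were known at the time.

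**What to change.** State in 8.1 and 8.2 that the two-sided exact test against 52% in all 40 patients, after the last 12-month MRI, is the only primary test, with success at 28/40 or more. State that any earlier report is preliminary and descriptive: ORR with an exact 95% confidence interval, the number of patients who have completed the 12-month MRI, and no claim of success. The stated alpha and 82% power then describe the test that decides.

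The cost is a short amendment, with no new patients or data. The early report carries a weaker claim. The version footer is dated 10/22/20, after the May 2020 target, so that report may already have been submitted; if so, the final report should describe it as a preliminary look. Waiting for the last 12-month MRI may also affect the calendar: a patient enrolled in mid-2021 with 14 months on study finishes around August 2022, later than the early-2022 closure anticipated in 8.1.

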8.2 Data Analysis

Descriptive statistics (median, min-max, range, and percentages) will be provided for the pretreatment data such as demographics and comorbidities, and post-treatment complications. To assess the 1-year response rate in patients, one-sample binomial test will be conducted. For the secondary objectives,

descriptive analysis will be applied to determine the median survival times and Kaplan-Meier survival curves will be plotted for the endpoints:

- Time to progression
- Progression-free survival
- Overall survival

All analysis will be performed using SAS version 9.3 (SAS Institute Inc., Cary, NC, USA).

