1.2 Primary Objectives

1.2.1 To determine the objective response rate up to 1 year in patients with HCC treated with combination TACE and SBRT.

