6.0 DATA COLLECTION

6.1 Before enrollment, patients will be interviewed and assessed for meeting inclusion and exclusion criteria. Patients will also be assessed for ability to complete the protocol and follow up. Follow up and data collection will proceed as outlined below and summarized in Appendix D.

6.1.1 Pretreatment data will include the following parameters:

1. Demographics: age, sex, etiology of liver disease
2. Past Medical History: comorbidities
3. Related symptomatology
4. Performance status according to ECOG
5. Liver and renal function tests: bilirubin, AST, ALT, albumin, alkaline phosphatase, GGTP, BUN, creatinine, Na, INR, and platelet count
6. Serum alpha fetoprotein (AFP)
7. Tumor MRI with Gd-EOB metrics: size, number of tumors, tumor location, tumor necrosis, mean ADC of whole tumor and viable component
8. Liver MRI metrics: degree of hepatobiliary phase enhancement, mean ADC
9. Chest CT

6.2 A regular on treatment visit (OTV) will be used to assess acute treatment related toxicity according to CTCAE v. 4. In the event that there is a treatment break, patients will be seen at least once a week.

6.3 Three to 6 weeks following completion of SBRT, the patient will be seen in routine follow up to assess and manage any post-treatment complications. At that time of the first visit, blood work will be obtained as follows:

Liver and renal function tests: bilirubin, AST, ALT, albumin, alkaline phosphatase, GGTP, BUN, creatinine, Na, INR, and platelet count
 Serum alpha fetoprotein (AFP)

6.4 Routine follow up will be scheduled every 3 to 4 months from the completion of radiation (2 to 3 months after the initial one month visit). For medical necessity, patients can be sooner. In addition to assessment of toxicity according to CTCAE, blood work will be obtained as follows:

Liver and renal function tests: bilirubin, AST, ALT, albumin, alkaline phosphatase, GGTP, BUN, creatinine, Na, INR, and platelet count
 Serum alpha fetoprotein (AFP)

6.5 Every 3 to 4 months post-radiation, the patient will have an MRI with Gd-EOB-DTPA to assess tumor response (as outlined below) up to one year.

6.6 Every 6 to 8 months, the patient will have a CT of the chest, abdomen, and pelvis to assess for systemic disease. If clinically warranted, imaging can be obtained sooner. PET/CT might be used if clinically warranted.

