6.7 If a patient received his/her TACE treatments and did not receive SBRT, he/she will nevertheless be followed by the same follow up schedule as above except for the OTVs and one month post-radiation visit.

6.8 Patients will be followed after one year per standard medical care.

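### Does the 82% power for 40 enrolled patients conflict with a primary objective set in patients treated with both TACE and SBRT?

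*Combined protocol and SAP*

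**What the plan says.** Section 1.2.1 gives the primary objective: "To determine the objective response rate up to 1 year in patients with HCC treated with combination TACE and SBRT". Section 8.1 reports that "we increased our target enrollment goal from 30 patients to 40 patients", and that "increasing the sample size to 40 patients yields 82% power with a type I error rate of 0.05". The test there is a two-sided exact test of one proportion, with a null response rate of 52%. The regimen is TACE plus SBRT, and the team will "continue to consider the proposed treatment regimen effective if it can improve the ORR to at least 75" percent. The section makes no allowance for attrition and gives no replacement rule.

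Section 6.7 covers patients who do not reach radiation: "If a patient received his/her TACE treatments and did not receive SBRT, he/she will nevertheless be followed by the same follow up schedule", "except for the OTVs and one month post-radiation visit". It gives no expected number. Section 4.3 places a laboratory check between TACE and SBRT, so an enrolled patient can end up on this path.

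Section 8.2 specifies the test: "To assess the 1-year response rate in patients, one-sample binomial test will be conducted". It does not say which patients, or how someone without SBRT counts. Section 6.5 times the response scans from radiation: "Every 3 to 4 months post-radiation, the patient will have an MRI with Gd-EOB-DTPA to assess tumor response".

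**The concern.** The number 40 is an enrolment figure in section 8.1, while section 1.2.1 describes a treated population. The two are the same set only if every enrolled patient goes on to SBRT, and section 6.7 shows that the team foresaw exceptions. If TACE-only patients are left out, both the denominator and the success cutoff change. If they stay in, the 82% requires a 75% response rate across all 40, including patients who never had the regimen.

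This is the only hypothesis test in the plan, so a verdict that depended on an unwritten choice would matter. Section 8.1 also says that primary analyses were already under way after the 30th enrolment, which raises the worry that the choice was made with data in hand. In addition, the scans are counted from SBRT, so a TACE-only patient seems to have no start date for the scans or for the year.

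**Working it through.** **Inputs.** From section 8.1: n = 40, null rate 0.52, target rate 0.75, two-sided exact test at 0.05. Assumed, because the documents give no figure: k = 1 to 4 of the 40 enrolled patients receive no SBRT, treated patients respond at 0.75, and TACE-only patients, where kept, respond at the plan's own null rate of 0.52.

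**Step 1: the plan's figure.** At n = 40 the smallest significant count is 28. P(X ≥ 28 | 40, 0.52) = 0.0160, and the two-sided p-value is 0.026 (minimum-likelihood) or 2 × 0.0160 = 0.032 (doubled tail). At 27 the p-values are 0.057 and 0.069. Power is P(X ≥ 28 | 40, 0.75) = 0.821. The stated 82% is correct.

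**Step 2: follow section 1.2.1 and analyse treated patients only.** Here n = 40 − k, the cutoff is the smallest significant count, and power is P(X ≥ cutoff | n, 0.75).

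| k | n | Cutoff | Power |
|---|---|---|---|
| 0 | 40 | 28 | 82.1% |
| 1 | 39 | 27 | 84.6% |
| 2 | 38 | 27 | 77.7% |
| 3 | 37 | 26 | 80.6% |
| 4 (minimum-likelihood p) | 36 | 25 | 83.3% |
| 4 (doubled-tail p) | 36 | 26 | 72.5% |

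The two p-value definitions agree for k = 0 to 3. They part at k = 4, where 25 of 36 has p = 0.044 under one definition and 2 × 0.0258 = 0.052 under the other. Power does not fall steadily with n, because the cutoff moves in whole patients.

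**Step 3: keep all 40, with TACE-only response as observed.** The cutoff stays at 28 and power is P(Bin(40 − k, 0.75) + Bin(k, 0.52) ≥ 28).

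| k | Power |
|---|---|
| 1 | 79.8% |
| 2 | 77.4% |
| 3 | 74.8% |
| 4 | 72.1% |

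**Step 4: how often the choice between steps 2 and 3 reverses the verdict.**

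| k | Only the treated set succeeds | Only the full 40 succeeds | Total |
|---|---|---|---|
| 1 | 4.7% | 0% | 4.7% |
| 2 | 2.8% | 2.5% | 5.3% |
| 3 | 7.0% | 1.2% | 8.1% |
| 4 (minimum-likelihood p) | 11.8% | 0.5% | 12.3% |
| 4 (doubled-tail p) | 4.7% | 4.2% | 8.9% |

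Totals come from unrounded values. From k = 2 the reversals run both ways. For example, 26 of 38 treated patients falls short of 27, yet two TACE-only responders bring the full set to 28 of 40.

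**Step 5: the harshest rule.** If TACE-only patients count automatically as non-responders, power is P(Bin(40 − k, 0.75) ≥ 28) = 74.7%, 65.6%, 55.0% and 43.6% for k = 1 to 4. Reversals against step 2 are then 9.9%, 12.1%, 25.6% and 39.7% (28.9% at k = 4 with the doubled-tail p), all in the direction of success for the treated set.

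**Step 6: the start date.** Section 8.1 says that follow-up with scans about every three months for up to a year begins once the treatments are over, without tying this to SBRT. Counting from the last treatment given is a workable reading of section 6.7 for a TACE-only patient.

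**The case for a change.** The strongest case for a change is that one primary test should have one written denominator. No passage says whether TACE-only patients are in it. The route to TACE only is real, since section 4.3 has a laboratory check and section 6.7 exists because the team foresaw the outcome. Under non-responder counting, 4 such patients would cut power from 82% to 44% and reverse the verdict in up to 40% of trials. With the first 30 patients already being analysed, writing the rule down would cost only a few sentences.

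The omission itself stands: section 8.2 names no set, and the 40 is an enrolment count. The size of the harm does not. Section 6.7 is conditional and implies no particular rate. No passage counts TACE-only patients as failures. Section 6.7 keeps them under follow-up, so their response would be seen, which brings the reversals down to step 4 and removes the one-way pattern from k = 2 onward. The 40% also depends on one definition of the p-value. That a rule was picked after seeing data is conjecture; section 8.1 says only that analyses were being done. An exclusion for tumours that cannot be dosed safely adds little, because section 6.1 has eligibility assessed before enrolment.

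The plain remedy would be to define the set as patients who had TACE and SBRT. That would restate the population section 1.2.1 already gives.

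**Conclusion.** No change to the plan is needed. Sections 1.2.1 and 8.1 differ in wording (treated against enrolled), and section 8.2 is silent, but the primary objective itself supplies the population. Testing treated patients against 52% at whatever number is treated keeps the exact test at its nominal level. Power is 78% to 85% for 1 to 3 assumed TACE-only patients, close to the stated 82%. At 4 it is 83% or 72.5%, according to the p-value definition. The 82% is not an error: it holds if all 40 receive SBRT, or if 75% is the rate expected in all 40.

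The remaining ambiguity, between leaving TACE-only patients out and keeping them as observed, reverses the verdict in about 5% to 12% of trials. That range rests on assumed counts of 1 to 4, 75% response in treated patients and 52% in the others. If several more patients missed SBRT, the loss would be larger, but the documents give no ground for expecting that. For a non-randomised pilot, this is missing detail that a competent analyst fills from section 1.2.1, reporting the number who did not reach SBRT.

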9.0 REGULATORY CONSIDERATIONS

9.1 Protocol Review and Amendments

This protocol, the proposed informed consent and all forms of participant information related to the study (e.g., advertisements used to recruit participants) and any other necessary documents must be submitted, reviewed and approved by a properly constituted IRB governing each study location.

Any changes made to the protocol must be submitted as amendments and must be approved by the IRB prior to implementation. Any changes in study conduct must be reported to the IRB. The MSSM Overall Principal Investigator (or Protocol Chair) will disseminate protocol amendment information to all participating investigators.

All decisions of the IRB concerning the conduct of the study must be made in writing.

9.2 Informed Consent

All participants must be provided a consent form describing this study and providing sufficient information for participants to make an informed decision about their participation in this study. The formal consent of a participant, using the IRB approved consent form, must be obtained before the participant is involved in any study-related procedure. The consent form must be signed and dated by the participant or the participant's legally authorized representative, and by the person obtaining the consent. The participant must be given a copy of the signed and dated consent document. The original signed copy of the consent document must be retained in the medical record or research file.

